### **8.3.2. Concentration-Response Relationship Analysis**

The data may be subjected to PK-PD modelling including retrospective assessment of dose- and exposure-response correlations. An additional advantage of this approach is that it allows the data to be included in further modelling and simulation analyses characterizing the effects of FAB122 on disease progression and enabling the development of a predictive model framework to support dose justification (including in special subpopulations) and aid in the optimization of the design of future clinical studies.

In case PK-PD modelling will be performed, the details of the PK-PD modelling will be described in a separate PK analysis plan.

## 9. SAFETY REPORTING

Adverse events will be recorded (using MEDRA version 24.0) beginning immediately after the ICF is signed. The investigator (and/or designee) must document all AEs reported by the subject from the signing of the ICF through completion of the final follow-up. Any subject who is withdrawn from the study due to an AE shall be followed until the outcome of the event is determined, and the investigator will document available follow-up information on the subject's database.

In this study, an external Data Safety Monitoring Board (DSMB) will be appointed to review all safety data generated during the study. For more details see section 13.2.1

### 9.1. Definitions

#### 9.1.1. Adverse Event

An AE is any unfavorable and unintended sign (including an abnormal laboratory finding), symptom, or disease temporally associated with the use of a medicinal (investigational) product, whether or not related to the medicinal (investigational) product. An AE is any symptom, sign, illness, or experience that develops or worsens in severity during the course of the study. Adverse events reported after consent but before the first dose of study drug are still to be documented by the investigator but will be considered non-treatment-emergent AEs.

Intercurrent illnesses or injuries should be regarded as AEs. Abnormal results of laboratory tests or diagnostic procedures are considered to be AEs if the abnormality:

- Is associated with clinical signs or symptoms
- Is considered by the investigator to be of clinical significance
- Results in study withdrawal
- Fulfils any of the criteria for a SAE, as described in this section
- Requires intervention or further evaluation to determine the etiology of the abnormality and/or assess the risk to the subject
- Requires treatment

Changes in ALS symptoms will not be documented as AEs unless they are extraordinary and/or unexpected. In the same way planned hospitalizations for procedures which are related to the patient's disease, and are expected within the evolution of the ALS symptoms (i.e. PEG procedure; Mechanical ventilation set up) will not be considered as SAEs unless they are extraordinary and/or unexpected and/or of they meet other seriousness criteria.

---

A treatment-emergent adverse event (TEAE) is defined as an adverse event observed after the first dose of study drug. If a subject experiences an event both prior to and after starting study drug administration, the event will be considered a TEAE (of the treatment) only if it has worsened in severity (i.e., it is reported with a new start date) after study drug administration of the specific treatment, and prior to the start of another treatment, if any.

#### **9.1.2. Adverse Reaction**

All noxious and unintended responses to a medicinal product related to any dose should be considered an adverse drug reaction. “Responses” to a medicinal product means that a causal relationship between a medicinal product and an adverse event is at least a reasonable possibility (e.g., the relationship cannot be ruled out).

#### **9.1.3. Unexpected Adverse Reaction**

An Unexpected Adverse Reaction is defined as an adverse reaction, the nature or severity of which is not consistent with the applicable product information. For FAB122, the reference safety information is included in the Investigator’s Brochure. The reference safety information will be reviewed yearly, and the periodicity of the review will be harmonized with the reporting period of the Development Safety Update Report.

#### **9.1.4. Adverse Event of Special Interest**

AESI (serious or non-serious) is one of scientific and medical concern specific to the sponsor’s product or program, for which ongoing monitoring and rapid communication by the investigator to the sponsor can be appropriate. Such an event might warrant further investigation in order to characterize and understand it. Depending on the nature of the event, rapid communication by the sponsor to other parties (e.g., regulators) might also be warranted.

For this study, any significant abnormalities detected in the NCS or any AE which might suggest neuropathy (e.g., numbness) should be considered an AESI and must be communicated appropriately to the sponsor and DSMB.

### **9.2. Severity Assessment**

The severity of each AE will be graded by the investigator according to the following criteria:

- Mild: awareness of sign or symptom, but easily tolerated
- Moderate: discomfort sufficient to cause interference with normal activities
- Severe: incapacitating, with inability to perform normal activities

### 9.3. Serious Adverse Event

A Serious Adverse Event (SAE) is any untoward medical occurrence at any dose that:

- Results in death
- Is life threatening
- Requires inpatient hospitalization or prolongation of existing hospitalization
- Results in persistent or significant disability/incapacity
- Is a congenital anomaly/birth defect
- Is a medically important event that may jeopardize the subject or may require medical or surgical intervention to prevent one of the other outcomes listed above

The term “life threatening” in the definition of “serious” refers to an event in which the subject was at risk of death at the time of the event; it does not refer to an event that hypothetically might have caused death if it were more severe. Death is an outcome of an event. The event that resulted in death should be recorded and reported on the SAE form and documented in the eCRF/study database.

Any hospital admission with at least 1 overnight stay will be considered an inpatient hospitalization. An emergency room or urgent care visit without hospital admission will not be recorded as an SAE under this criterion, nor will hospitalization for a procedure scheduled or planned before signing of informed consent, or elective treatment of a preexisting condition that did not worsen from baseline. However, unexpected complications and/or prolongation of hospitalization that occur during elective surgery should be recorded as adverse events and assessed for seriousness. Admission to the hospital for social or situational reasons (ie, no place to stay, live too far away to come for hospital visits, respite care) will not be considered inpatient hospitalizations.

### 9.4. Assessment of Causality

The Investigator must determine the relationship between the administration of investigational product and the occurrence of an AE/SAE as Unrelated, Unlikely related, Possibly related or Probably related as defined below:

Unrelated or Unlikely related: Means a causal relationship of the adverse event to investigational product administration is **unlikely or remote**, or other medications, therapeutic interventions, or underlying conditions provide a sufficient explanation for the observed event.

Event can be readily explained by other factors such as the

---

		subject's underlying medical conditions, concomitant therapy, or accident; or there is no temporal relationship between study drug or procedure and the event.
		A reasonable possibility or clinical evidence that the study drug or procedure caused the event is lacking.
Possibly Probably related:	or	Means there is a reasonable possibility that the administration of investigational product caused the adverse event. 'Reasonable possibility' means there is evidence to suggest a causal relationship between the investigational product and the adverse event.
		
The AE follows a reasonable temporal sequence from administration of the study drug or procedure and at least one of the following instances of clinical evidence:
 

• Follows a known or suspected response pattern to the study drug or procedure.

• Is confirmed by improvement upon stopping the study drug, i.e., after single dose (dechallenge).

There is a reasonable possibility that the study drug or procedure caused the event—i.e., there is evidence to suggest a causal relationship. In such case, the AE is considered an *adverse reaction* (AR). A *suspected* AR has a lesser degree of certainty about causality than an AR.

- Causality should be assessed and provided for every AE/SAE based on currently available information. Causality is to be reassessed and provided as additional information becomes available.

## 9.5. Reporting Adverse Events

All AEs (regardless of seriousness or relationship to study drug) including those from the time of signing of the ICF through to the follow-up/early withdrawal visit are to be recorded in the subject's source documents and on the corresponding page(s) in the database. Whenever possible, symptoms, signs, and laboratory abnormalities should be grouped as a single syndrome or diagnosis. The investigator should specify the date of onset, severity, action taken with respect to study drug, corrective treatment/therapy given, outcome and his/her opinion as to whether there is a reasonable possibility that the AE was caused by the study drug, according to the definitions noted above. All medications administered to treat an AE must be recorded in the subject's source documentation and documented in the database.

## 9.6. Reporting Serious Adverse Events

Reporting of SAEs will be conducted in accordance with the appropriate regulatory guidelines. All SAEs that occur from the time of signing the ICF to the follow-up/early withdrawal visit must be reported, whether or not the event is considered associated with the study drug. SAEs must be reported, via eCRF, within 24 hours of site awareness. Safety reporting information and contact numbers will be provided to the clinical site.

The investigator must complete the SAE Reporting Form in English and submit it via eCRF, with other relevant source documentation, to the medical monitor [[contact]](mailto:[contact]) and the sponsor's Pharmacovigilance (PV) representative within 24 hours of awareness of the event to:

[name] (Head of PV team, Pharmalex)

[contact] / [contact]

Email: [[contact]](mailto:[contact])

The investigator must also provide with urgent priority (upon receipt of a request) other relevant documentation (e.g., copies of diagnostic test results, hospital discharge summary, and/or autopsy report) and send this information to the sponsor's medical monitor.

All SAEs and medications administered in association with SAEs must be recorded in the study database. The investigator must also promptly notify the Independent Ethics Committee (IEC) of SAEs, including any follow-up information, in accordance with local institutional policy and applicable regulatory requirements.

The responsible medical monitor at the Sponsor will evaluate causality and expectedness of SAEs and in case of a suspected unexpected serious adverse reaction (SUSAR), such information will be sent to the sponsor's PV representative for review.

### 9.6.1. Adverse Event Follow-up

The investigator should take all appropriate measures to ensure the safety of the subjects, including referral to a specialist if indicated. The investigator should follow up on the outcome of any AE until the return to normal or stabilization of the subject's condition.

In case of an SAE, the subject must be followed up until clinical recovery is complete and laboratory results have returned to normal, or until the condition becomes chronic in nature, stabilizes (in the case of persistent impairment), or the patient dies. This implies that follow-up may continue after the subject discontinues from the study and that additional information may be requested.

Any SAE brought to the attention of the investigator any time after cessation of study drug and considered by him/her to be caused by the study drug with a reasonable possibility, should be reported through the SAE reporting process.

---

Within 24 hours of receipt of follow-up information, the Investigator must update the SAE form and submit it by email or fax with other relevant source documentation to the sponsor's Pharmacovigilance (PV) representative.

### **9.7. Expedited Reporting**

Competent authorities will be notified of any AE associated with the use of the study drug that is both serious and unexpected, in accordance with the appropriate local regulatory guidelines.

The sponsor's PV representative will report all relevant information about SUSARs that are fatal or life-threatening as soon as possible to the applicable competent authorities in all the countries concerned, and to the Central Ethics Committee concerned (if applicable), in any case no later than 7 days after first knowledge by the Sponsor/designee of such a case, followed by a period of maximum of 8 days to complete the initial preliminary report. All other SUSARs will be reported within a period of maximum 15 days after the sponsor/designee has first knowledge of the SAE.

The Sponsor/designee will also report any additional expedited safety reports required in accordance with the timelines outlined in country-specific legislation.

The Sponsor/designee will also inform all Investigators as required per local regulation.

Events associated with placebo will usually not satisfy the criteria for a SUSAR and therefore for expedited reporting.

### **9.8. Unblinding**

This study will be performed in a double-blind fashion. The randomization list will not be available to the investigator, study staff, subjects, sponsor, or monitor. The investigational drug and its matching placebo are indistinguishable and will be packaged in the same way. Treatment emergency codes should not be broken except in emergency situations i.e., in case of a medical emergency or in the case a SUSAR occurs, the investigator or the sponsor's Unblinding Manager, will break the patient's code, through interactive web response system (IWRS), and if possible, the sponsor should be contacted before the emergency code is opened.

The investigator should only unblind the treatment allocation in the course of a clinical trial if this is relevant to the safety of the subject.

As regards the sponsor, when an event may be a SUSAR the blind should be broken by the sponsor only for that specific subject. The blind should be maintained for persons responsible for the ongoing conduct of the study (such as the management, monitors, investigators) and those responsible for data analysis and interpretation of results at the conclusion of the study, such as biometrics personnel. Unblinded information should only be accessible to those who need to be involved in the safety reporting to national competent authorities, Ethics Committees and Data Safety Monitoring Boards (DSMB), or persons performing ongoing safety evaluations during the trial.

---

It should be noted that unblinding is not necessarily a reason for patient's discontinuation and the patient could continue the study treatment and procedures after unblinding. Furthermore, patient's death will not be considered a systematic reason for unblinding and will only be performed if deemed necessary or requested by the IEC and/or CA.

The Unblinding Manager contact details are:  
[name] (Head of PV department, Pharmalex)  
[contact]  
Email: [contact]

#### **9.9.      Pregnancy**

If a patient becomes pregnant during the study or within the safety follow-up period defined in the protocol, the Investigator is to stop dosing with study drug(s) immediately and the patient should be withdrawn from the study. Early termination procedures should be implemented at that time.

A pregnancy as such is not an AE, however, it must be reported to the Sponsor within 24 hours of knowledge of the event completing a Pregnancy Reporting Form.

Female patients will be instructed to notify the investigator immediately if they become pregnant during the study. Male patients will be instructed to notify the investigator immediately if their partner becomes pregnant. Pregnant patients will be withdrawn from further study treatment. The patients will also be instructed to report pregnancies discovered after the last visit, if they believe that conception occurred during their participation in the study.

The pregnant patient or partner will be followed until the end of the pregnancy. Any complication during the pregnancy should preferably be reported as an AE. The outcome of the pregnancy must be reported on the Pregnancy Reporting Form. Any spontaneous abortion, stillbirth, birth defect/congenital anomaly, death, or other serious infant condition must be reported and followed up as an SAE. If the pregnancy outcome meets seriousness criteria the both the SAE form and pregnancy form should be forwarded.

## 10. HEALTH ECONOMICS

ALS is a devastating neurological disease for which there is no cure. The disease results in a progressive impairment in activities of daily living, including walking, eating and speaking. As a result, there is a significant negative impact on the quality of life of both patients and their families with associated considerable economic burden.

Expenses associated with the disease can be divided into direct and indirect costs. Direct costs are those expenses requiring payment, whether by the patient, government or a third-party payer (i.e., health insurance and non-profit-organizations), such as those associated with formal health care, medications, equipment, home or vehicle adaptations, medical devices, mobility aids and services. Direct costs can be further divided into healthcare costs and non-healthcare costs. Indirect costs represent opportunity loss, most notably lost income due to a patient's illness related absence from work or the voluntary caregiver duties taken on by family or friends. Both direct and indirect costs can overwhelm the financial resources of patients and their families and should be considered when evaluating the overall economic burden of ALS.

In this study, an exploratory cost-utility analysis for treatment with FAB122 will be conducted using the following data:

- Cost questionnaire: Data provided by a specific questionnaire for the direct and indirect costs associated with the disease (see annex 5). The consented patients will complete the questionnaire at baseline and every 12 weeks up to the end of the study.
- eCRF: Some data will be gathered from the patient's dataset such as hospitalizations, concomitant medications, and occurrence of AEs.

The following cost parameters will be considered for the cost-utility analysis among study groups:

1. Number of visits classified per specialist and type of visit (scheduled vs not scheduled).
2. Number of hospitalizations related to ALS classified per unit of stay and length of stay.
3. Medication and administration cost (inpatient vs outpatient).
4. Specialized equipment / Devices cost (i.e. mechanical ventilation-invasive or not, artificial nutrition – percutaneous endoscopic gastrostomy).
5. Number of new orthopaedic devices (i.e. wheelchair).
6. Paramedical treatment visits (i.e. physical therapy, rehabilitation, occupational therapist, speech and language therapist, or otherwise specified by the patient).
7. Formal care (i.e. health professional) and informal care (i.e. familiar/friend).
8. Employment situation.
9. Occurrence of AEs in each group.

An ad-hoc cost questionnaire will be completed at Baseline and weeks 12, 24, 36, 48, 60 and 72 via a study App or online questionnaire.

After the end of the study, analysis of each category will be done, then costs will be calculated by category and for all categories per patient. Costs would be calculated according to local tariffs and according to guidelines for cost analysis in healthcare research. All costs will be presented in euros.

## 11. STATISTICS

### 11.1. Statistical Analysis Plan (SAP)

The statistical analysis will be carried out in accordance with the principles specified in the International Conference on Harmonization (ICH) Topic E9. A detailed Statistical Analysis Plan (SAP) will be made available before the un-blinding of the data base.

The plan for the pharmacokinetic analysis will be fully detailed in the pharmacokinetic analysis Plan (PAP) that will be finalized before data base closure.

All statistical analyses will be performed using SAS Version 9.4 or higher (SAS Institute, Cary, NC 27513).

### 11.2. Sample Size Determination

The sample size estimation is based on the primary endpoint: the change from baseline in ALSFRS-R score after 48 weeks. A difference of 3.0 points between FAB122 treatment arm and placebo is assumed with a (pooled) standard deviation of 7.5 and an allocation ratio of 2:1 (FAB122:Placebo). With these assumptions, a total sample size of 300 (200 patients on FAB122 and 100 on placebo) is needed to achieve 90% power to detect the difference of 3.0 points between the two treatment groups at a 5% (2-sided) level of significance.

The standard deviation of 7.5 is based on recent study results with edaravone using a similar trial population as applied in this trial, where standard deviations varied between 3.4 and 6.9 (The Writing Group on behalf of the Edaravone (MCI-186) ALS 19 Study Group. 2017 b, 2017;). The variability in this study can be expected to be somewhat higher due to the change of formulation and due to the fact that in this study patient can use riluzole as background therapy.

The hypothesis in this study includes detection of a difference of 3 points in ALSFRS-R at week 48 between the two treatment arms. The patients in the placebo group in ALS studies typically deteriorate by 1 point per month, so 12 points in 12 months. A difference of 3 points therefore corresponds to a 25% difference in deterioration, which is considered clinically significant.

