### 11.4. Study Estimand and Handling of Missing Data

To be noted that in this study all efforts will be made to ensure collection of data up to week 48 for all randomized subjects and at least for 100 subjects up to week 72 regardless of treatment withdrawal or protocol deviations.

As per the ICH E9(R1) (*draft addendum on estimands and sensitivity analysis in clinical trials*), the plan for the assessment of the Primary endpoint (PEP) is described here after using the 4 attributes of the estimand:

1. Population: ALS patients fulfilling the selection criteria, as described in section 5 of this protocol
2. Primary endpoint (PEP): Change from baseline in Amyotrophic Lateral Sclerosis Functional Rating Scale – Revised (ALSFRS-R) score after 48 weeks (see sections 3.2.1 and 11.3.4.1)
3. Intercurrent events (IE): The assumptions and expectations on the relevant intercurrent for this study have been based on the publication of a similar trial (Cudkowicz et al., 2013)
4. Accordingly, the following situations have been identified:
  - a. No treatment initiation with the IMP: exclusion from the main analysis with the mFAS population.
  - b. Treatment discontinuation because of adverse events: expected rates  $\approx 3$  (control arm) - 7% (experimental arm).
  - c. Treatment discontinuation because of lack of efficacy: expected rates  $\approx 5$  (control arm) 10% (experimental arm).
  - d. Other treatment related reasons (i.e. due to efficacy or safety issues). To this category will apply other treatment related reasons that those specified in "b" and "c", even that, *a priori*, no potential scenarios are foreseen at the moment of the planning.
  - e. Rescue medication. No clear prevalence rates can be ascertained, but differential higher rates are expected in placebo. This situation is likely to be closely related to IE #c.
  - f. Non treatment-related reasons, others than specified in this list of IE: very low expected rates (i.e.  $\le 1\%$ ). This will also situations like patients moving (not because bad prognosis) to another location or death for completely treatment-unrelated reasons.
  - g. Related death (or death with unknown reasons): it is expected that the rate of death at 52 weeks will be lower than the observed in that trial ( $< 17\%$ ). A non-substantial but lower rate is expected in the experimental arm.

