The primary strategy for handling the IE will consist of the "Treatment Policy" strategy applied for all these intercurrent events, i.e., the efficacy observed assessment will be used regardless of the intercurrent event. Therefore, overall the amount of missing data generated will be a very small. For these cases a placebo (copy from reference) multiple imputation will applied. A total of 20 imputed data sets will be created.

However, it is noted that the "Treatment Policy" strategy will not be applicable for terminal intercurrent events such as death (IE #g) or when there are real lost to follow-up cases after doing all efforts to retrieve the data (some cases in IE #f). For cases with missing data in IE #f, the same general approach as described above will be implemented. For related death (IE #g) it is proposed to use a "Composite strategy" and thus a conservative scenario using a 95th worst percentile combined with multiple to avoid variance artefactual shrinking.

---

- h. Population-level summary: the change from baseline in ALSFRS-R score after 48 weeks (primary time point), using a linear mixed modelling for repeated measures. The model will include factors for treatment, time, treatment-by-time interaction, and concomitant use of riluzole (yes/no) as fixed effects and baseline ALSFRS-R score and slope of disease progression (based on change in ALSFRS-R score) as (random) covariates (see section 11.3.4.1)).

To evaluate the impact of missing data and of the handling methods, a number of sensitivity analyses will be performed for the primary endpoint:

- **As treatment multiple imputation:** For any subject with missing values, the estimates for the missing assessments will be based on the actual treatment group of that subject. One hundred imputations will be performed.

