The “Composite” strategy for handling these events will be applying a conservative scenario using the 95% worst percentile combined with multiple imputation (the intercurrent event is explicitly taken into account and made part of the outcome by this imputation, conditioned on timepoint). This method uses the imputation of a conservative value representing the 95th worst percentile.

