### **5.6.1 Primary analysis**

The primary endpoint is defined as the change from baseline in total ALSFRS-R score after 48 weeks (primary timepoint).

For the primary analyses, a placebo (reference) multiple imputation (pMI) will be applied to impute missing data for any patients (i.e. from both treatment arms) who discontinue treatment early, irrespective the reason for drop-out (only when due to intercurrent events with unknown cause), and for which no data was collected after treatment discontinuation. The pMI method assumes the statistical behavior of placebo- and drug-treated patients after dropout is the statistical behavior of placebo-treated patients. A total of 20 imputed data sets will be created.

Before applying the statistical model to the primary endpoint, intercurrent events will be handled following the rules specified in Section 5.2.

The primary endpoint will be analyzed using a mixed model for repeated measures (MMRM), considering ALSFRS-R is assessed at multiple timepoints. The average treatment effect (lsmeans) and the treatment difference (estimand) of the change from baseline ALSFRS-R total score at 48 weeks will be extracted from the results from this model and presented together with the 95% confidence interval and p-value. Other timepoints will also be presented.

The model will include factors for treatment, time, treatment-by-time interaction, the stratification factor concomitant use of riluzole (yes/no), baseline ALSFRS-R score and the stratification factor slope of disease progression as fixed effects. An unstructured (UN) covariance matrix will be used in the model. If the model does not converge, the structure will be adapted to respectively AR(1), Toeplitz or Compound Symmetry (CS). The results of the 20 imputed data sets will be combined to obtain the final estimate of the treatment difference with 95% confidence interval and p-value.

An example SAS code which can be used as basis is as follows:

```
proc mixed data=<data>;
  class trt time riluse;
  model cfb=trt time trt*time riluse base disslope / ddfm=kr;
  repeated time/ subject=patient type=un;
  lsmeans trt*time/cl;
run;
```

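### The 90% power holds only for 300 fully observed patients; no allowance is stated for the expected discontinuations and deaths or for how the primary analysis scores them

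*Protocol*

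**What the plan says.** **The calculation.** Protocol 11.2: "A difference of 3.0 points between FAB122 treatment arm and placebo is assumed", with SD 7.5, 2:1 allocation and a test "at a 5% (2-sided) level of significance". From this, "a total sample size of 300 (200 patients on FAB122 and 100 on placebo) is needed to achieve 90% power". SAP 2.4 repeats the figures and refers back to the protocol for their background. The SD is set above the 3.4 to 6.9 seen in the source study, and the reasons given are the new formulation and background riluzole.

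**The expected events.** Protocol 11.4 expects treatment discontinuation of about 3% (control) and 7% (active) for adverse events, and about 5% and 10% for lack of efficacy. On deaths, "it is expected that the rate of death at 52 weeks will be lower than the observed in that trial", with that trial's rate given as 17% and a slightly lower rate expected on active treatment.

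**How they are handled.** Treatment policy applies to discontinuation, so scores taken off treatment are used, and the protocol concludes that "overall the amount of missing data generated will be a very small". Discontinuers without later data are imputed from placebo. SAP 5.6.1: "The pMI method assumes the statistical behavior of placebo- and drug-treated patients after dropout is the statistical behavior of placebo-treated patients". Deaths, and in the SAP also real losses to follow-up, are handled by "applying a conservative scenario using the 95% worst percentile combined with multiple imputation" (SAP 5.2).

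**The concern.** The power calculation and the primary estimand were written separately. The first treats every patient as having a week 48 score from one normal distribution per arm, with means 3.0 apart. The second expects some patients to stop treatment, more of them on FAB122, and some to die and receive a score far down the scale. Stopping can shrink the mean difference. Scoring deaths at an extreme value widens the spread and, unless deaths are sufficiently fewer on FAB122, also shrinks the difference. With only 3 patients beyond the 297 needed, there is nothing in N to absorb either.

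At stake is how the result is read. A null primary result would be judged against a 90% that the planned analysis may not have, and the first step of the testing hierarchy also controls whether the key secondary tests are confirmatory.

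**Working it through.** **Inputs from the documents.** Difference 3.0, SD 7.5, 200 and 100 patients, two-sided 5% (Protocol 11.2, SAP 2.4). Discontinuation for the two named reasons: 7% + 10% = 17% on FAB122 and 3% + 5% = 8% on placebo (Protocol 11.4). Placebo patients have no drug effect to lose, so only the 17% matters for dilution.

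**Assumptions, not in the documents.** Deaths by arm (FAB122/placebo) of 4%/5% or 9%/11%. The 17% lose none, half or all of the 3.0 points. The 3.0 is the on-treatment effect. The test is unadjusted. For the hand calculation the placebo mean is -12 and the FAB122 mean -9. Deaths are scored at -12 - 1.645 × 7.5 = -24.34.

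**1. The plan's figure.** Placebo n = (1.960 + 1.282)² × 7.5² × (1 + 1/2) / 3.0² = 98.5, so 99, and 297 in total. At 200/100, SE = 7.5 × √(1/200 + 1/100) = 0.919. Power = Φ(3.0/0.919 - 1.960) = 90.4%, or 90.2% by noncentral t. The figure reproduces.

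**2. Discontinuation alone.** Difference = 3.0 × (1 - 0.17 × share lost).
- Half lost: 2.745, power 84.6% (noncentral t).
- All lost: 2.49, power 77.1%.
- If only about 4% of the FAB122 arm became placebo-like, power would be about 88%.

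**3. Deaths of 9%/11%, no dilution.**
- FAB122 mean = 0.91 × (-9) + 0.09 × (-24.34) = -10.38. Placebo mean = 0.89 × (-12) + 0.11 × (-24.34) = -13.36. Difference 2.98.
- FAB122 variance = 0.91 × 56.25 + 0.91 × 0.09 × 15.34² = 70.5. Placebo variance = 0.89 × 56.25 + 0.89 × 0.11 × 12.34² = 65.0.
- SE = √(70.5/200 + 65.0/100) = 1.001. Power = Φ(2.98/1.001 - 1.960) = 84.5%.

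**4. The same, with the surviving 17% losing half.** The mean of FAB122 survivors becomes -9 - 0.17 × 1.5 = -9.255. The difference is 2.74, the SE 1.000 and the power 78.4%.

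**5. Summary** (SD 7.5, unadjusted)

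| Deaths FAB122/placebo | Benefit lost by the 17% | Power, by hand |
|---|---|---|
| none | none | 90.4% |
| 4%/5% | none | 87.9% |
| 9%/11% | none | 84.5% |
| 9%/11% | half | 78.4% |
| 9%/11% | all | 70.9% |

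Setting deaths to the 5th percentile of pooled survivors instead, by simulation, gives 85-87%, 78-80% and 70-73% for the three 9%/11% rows. Rounded working values are therefore about 88-89% for 4%/5%, and about 85%, 79% and 71% for 9%/11%.

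**6. Offsets, in the 9%/11%, half-loss case.** A true SD of 6.9 gives about 84-85%. Covariate adjustment with an assumed correlation of 0.3 gives about 81-82% at SD 7.5.

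**The case against.** The strongest reply is that the 17% is a rate of stopping treatment, not of missing data. Patients who stop stay on the visit schedule, and those who cannot attend give the ALSFRS-R by telephone. Placebo imputation covers only discontinuers with no later data, and SAP 5.6.1 limits it further to events of unknown cause. This stands. It makes the total-loss case (about 71%) an extreme rather than a planning value, since every discontinuer would have to lose the whole benefit. It does not restore 90%. Treatment policy does not stop benefit fading off drug; the fading then appears in observed scores. Nor can deaths be followed: at 9%/11% they alone bring power to about 85%.

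Second, the SD of 7.5 exceeds the largest source value, and the model adjusts for baseline score, progression slope and riluzole use. Both could help, as step 6 shows. But the protocol gives the SD margin other reasons, and neither offset alone returns the half-loss case to 90%.

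Third, Protocol 11.2 does not say that 3.0 is an on-treatment effect. It derives it as 25% of a placebo decline of 12 points in 12 months. If 3.0 is already the difference for the full estimand, the dilution must not be counted again. The wider spread from death scoring would remain: in step 3, Φ(3.0/1.001 - 1.960) is about 85%.

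A reader might infer that the plan's own figures imply a power of 71-87%. They do not. That range needs per-arm death rates and a share of benefit lost, and the documents give neither.

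**Conclusion.** The point holds as an unstated assumption, not as a calculation error. The 90% is correct for complete data and no deaths. The documents do not connect it to the discontinuation and death rates they expect, or to the scoring of deaths.

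The size depends on assumptions. Power stays near 88-89% if deaths are few (4%/5%) and the benefit persists off treatment. It is about 85% at 9%/11% deaths without dilution, and about 79% if the 17% lose half the benefit. These figures assume SD 7.5, an unadjusted test, 3.0 as the on-treatment effect and one fixed low score for deaths. The SAP's rule, conditioned on time point and combined with multiple imputation, is more elaborate and was not modelled.

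Two stronger readings are not supported: that the planned analysis is known to lack 90% power, and that 300 patients are too few. Both need event rates and an effect definition that the documents leave open.

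**What to change.** Keep N at 300. In Protocol 11.2 and SAP 2.4:

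1. Say that 90% applies with complete week 48 data and no deaths.
2. State whether 3.0 points is the on-treatment difference or the difference for the primary estimand.
3. Add the power of the planned primary analysis, with its imputation, death scoring and covariates, under explicitly stated discontinuation and per-arm death rates. An example is about 79-85% at deaths of 9% (FAB122) and 11% (placebo), with half to none of the benefit lost by the 17% who stop.

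This needs wording and a short simulation. No patient, endpoint or test changes. The only cost is a less favourable stated power.
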